vorapaxar 2.5mg od; 2) prasugrel/ticagrelor plus vorapaxar 2.5mg od; 3) continue DAPT with aspirin and prasugrel/ticagrelor. Randomized treatment will be administered for 30 ± 3 days; prasugrel and ticagrelor will be administered at their standard maintenance dose (10mg od and 90mg bid, respectively). Randomization will be stratified according to type of P2Y₁₂ inhibitor, in order to include at least 35% of patients on prasugrel. The rationale for predicting a higher number of randomized patients on ticagrelor derives from the more broad clinical indications of ticagrelor compared with prasugrel. Patient who entered the study before being on DAPT for 2 weeks will be required to complete 2 weeks of DAPT with aspirin and prasugrel/ticagrelor before randomization.

Blood sampling for PD testing will be conducted at 3 time-points: a) baseline (while patients will be on standard DAPT prior to initiating randomized treatment); b) after 7-10 days of randomized study treatment; c) after 30 ± 3 days of randomized study treatment. At each time point, blood will be collected before the morning dose of prasugrel/ticagrelor and vorapaxar, in order to measure trough levels of platelet inhibition. During study treatment in-hospital major adverse cardiac events (death, MI, stroke, and urgent revascularization procedures) and serious adverse events (bleeding and other adverse events) will be collected. Bleeding will be defined by the BARC (Bleeding Academic Research Consortium) definition [19].

After study completion, patients will resume antiplatelet treatment regimen at the discretion of the treating physician. A flow diagram of the study design is illustrated below.

Laboratory assessments

Peripheral venous blood samples (20 mL) will be drawn through a short venous catheter inserted into a forearm vein and collected in citrate, EDTA, and serum tubes as appropriate for assessments. The first 2-4 mL of blood will be discarded to avoid spontaneous platelet activation. Blood sampling for PD will be performed at 3 time points as indicated above in the study design section. Various PD assays will be performed as described below. Given the potential interplay between PAR-1 and P2Y₁₂ mediated signaling, assessments specific for both pathways will be conducted [11]:

1. Light transmittance aggregometry (LTA)
2. Thrombelastograph Coagulation Analyzer TEG 6s Series system (CORA[®] system)
3. Whole blood vasodilator-stimulated phosphoprotein (VASP)
4. Serum thromboxane B2

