4) Serum thromboxane B2: The concentration of serum thromboxane B2 (TXB2) will be measured by using the TXB2 EIA kit (Cayman Chemical Company, Ann Arbor, MI) according to the instructions of the manufacturer, as previously described [24]. Briefly, samples will be diluted with EIA buffer to bring their concentrations within the range of the standard curve. No other purification will be performed on any of the samples. A standard curve will be established by serial dilution of TXB2 between 1000 pg/mL and 7.8 pg/mL using EIA buffer as the matrix. The concentration of TXB2 in the samples will be calculated from a logistic 4-parameter fit of the standard concentrations versus percentage bound/maximum bound.

Study endpoints and sample size calculation

The primary end point of our study is the comparison of CAT-induced MPA between DAPT and DAPT plus vorapaxar after 30 ± 3 days of treatment. We hypothesize that adjunctive vorapaxar will result into a significant reduction of platelet aggregation. Assuming a 10% absolute reduction in CAT-induced MPA with a common standard deviation of 13%, 37 patients per group will be needed to detect a significant difference between DAPT and DAPT plus vorapaxar with a 90% power and 2-sided $\alpha=0.05$. Considering a possible 30-35% rate of invalid results due to hemolysis or drop-out and the three arms of treatment up to 146 patients will need to be randomized. Since there are no preliminary data in this particular setting, the sample size of our study was calculated based on previous data of vorapaxar in addition to DAPT with aspirin and clopidogrel [21]. This approach is in agreement with recommendations for pilot investigations [25].

Our secondary outcome will be the comparison of CAT-induced MPA between vorapaxar in addition to a new generation P2Y₁₂ receptor inhibitor (prasugrel or ticagrelor) and vorapaxar in addition to standard DAPT (aspirin and prasugrel/ticagrelor). We hypothesize that stopping aspirin will not lead to significant differences in CAT-induced MPA after 30 ± 3 days of treatment.

Other objectives will include the comparisons among the 3 groups of all PD parameters measured by multiple assays at every time point, as well as intragroup comparisons of PD parameters in order to evaluate the variability over time of vorapaxar PD effects, as well as how PD measures will be affected by aspirin withdrawal.

Statistical analysis plan

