Categorical variables will be expressed as frequencies and percentages. Continuous variables will be presented as mean \pm SD or median [IQR]. Continuous variables will be analyzed for normal distribution with the Kolmogorov-Smirnov test. Comparisons between categorical variables will be performed using two-tailed Fisher's exact test or the Pearson's chi-square test. Student's t test, Mann-Whitney U-test and Wilcoxon test will be used to compare continuous variables when appropriate. An analysis of covariance (ANCOVA) method with a general linear model, using baseline variables significantly different between groups as covariates, will be used to evaluate the overall difference between groups and all between-groups comparisons, in line with other PD studies [23]. Analysis of variance (ANOVA) will be used to evaluate intragroup comparisons. A 2-tailed p value of < 0.05 is considered to indicate a statistically significant difference for all the analyses performed. Statistical analysis will be performed by our group using SPSS v22.0 software (SPSS Inc. Chicago, IL).

Publication Strategy/Additional Information

Study subjects will be identified first (months 1-24): we expect to enroll approximately 5-6 subjects monthly and complete enrollment in 24 months (total: 126 subjects enrolled). Months 25-26 will be implied for statistical analysis and months 27-28 for manuscript preparation. We intend to present data at a major scientific meeting at completion of the study.

We anticipate no major problems with the described protocol since the approach is a straight forward prospective study and is based on well-established methods. However, since there is limited experience with vorapaxar to define platelet function, variability may be higher than expected and we cannot currently perform a detailed sample size calculation. We anticipate adding this to the protocol after inclusion of the study population has been completed. If the sample size after one year is estimated to be too small, additional patients will be included. This approach is in agreement with recommendations for pilot investigations [25].

Possible Discomforts and Risk

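### Within-arm changes over three visits are assigned to an unspecified ANOVA; both usual readings give less power than the data allow, for an exploratory objective only

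*Combined protocol and SAP*

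**What the plan says.** Research Design: "Blood sampling for PD testing will be conducted at 3 time-points", namely baseline on standard DAPT, day 7-10 and day 30 ± 3 of randomized treatment. The same patients are sampled each time.

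Study endpoints and sample size calculation: below the primary and secondary outcomes, the other objectives include "intragroup comparisons of PD parameters in order to evaluate the variability over time of vorapaxar PD effects", together with how the measures respond to aspirin withdrawal. The same section expects 30-35% of results to be lost to hemolysis or drop-out, and does not say whether that rate is per patient or per sample.

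Statistical analysis plan: one sentence gives the method for this objective, "Analysis of variance (ANOVA) will be used to evaluate intragroup comparisons". Just before it, a general sentence reads "Student's t test, Mann-Whitney U-test and Wilcoxon test will be used to compare continuous variables when appropriate". No repeated-measures form, covariance structure, sphericity correction, visit contrast or rule for invalid samples is given. The software is SPSS v22.0, with no procedure named.

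**The concern.** Three values from one patient are correlated, and a good share of them is expected to be missing. The word ANOVA has two usual readings here, and each has a cost.

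- **One-way ANOVA** treats the visits as separate groups of patients. Differences between patients stay in the error term, so the standard error of a change is too large and the test is conservative.
- **Classical repeated-measures ANOVA** removes the between-patient variation but drops any patient with one missing or invalid sample.

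At stake is the precision with which the trial can say how stable the vorapaxar effect is from day 7-10 to day 30, and how far the measures move from baseline. Modest changes may go undetected although the data could have shown them.

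**Working it through.** **1. The plan's own figure.** The plan assumes a 10-point difference "with a common standard deviation of 13%, 37 patients per group will be needed", at 90% power and two-sided 0.05. The normal approximation gives n = 2 × (1.960 + 1.282)² × 13²/10² = 35.5, so 36 per group. With the t distribution, power is 89.6% at 36 and 90.4% at 37. The stated 37 is confirmed. It is a between-arm figure; the plan gives no power for within-arm change.

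**2. Ignoring the pairing.** Take two visits, complete data, SD 13, n = 37. The within-patient correlation r is not in the documents and is assumed to lie between 0.3 and 0.7.

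- Standard error used by the unpaired test: 13 × √(2/37) = 3.02.
- True standard error: 3.02 × √(1 − r).
- Ratio 1/√(1 − r): 1.20, 1.41 and 1.83 at r = 0.3, 0.5 and 0.7, an overstatement of 20%, 41% and 83%.
- True type I error at r = 0.5: the critical value 1.993 becomes 1.993/√0.5 = 2.82 on the true scale, a two-sided probability of about 0.5% instead of 5%.
- Observed change needed for significance: 1.993 × 3.02 = 6.02 points. Against a true 10-point change, power is still 94%, 97% and 99% at the three correlations.

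**3. Complete cases.** Up to 146 patients in three arms is 146/3, about 49 per arm.

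- Loss per patient: 49 × 0.70 = 34 and 49 × 0.65 = 32 remain.
- Loss independent at each visit: 49 × 0.70³ = 17 and 49 × 0.65³ = 13 remain.

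The first is the more natural reading, because the rate is used to inflate the number of patients for an endpoint at a single visit. Publication Strategy/Additional Information gives 126 enrolled instead of 146. That is 42 per arm, of whom 42 × 0.65 = 27 to 42 × 0.70 = 29 would be complete under per-patient loss.

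**4. Power with three visits and missing samples.** Simulation: 48 patients in one arm, SD 13, equal correlation between visits, 32.5% loss completely at random, 1,500 runs per cell. Per-patient loss here means that 32.5% of patients have one bad sample. The mixed model is given the true covariance, so its figures are slightly optimistic. Entries are one-way / complete-case repeated-measures / mixed model, for a drop held at both later visits.

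| Change | Loss | r = 0.3 | r = 0.5 | r = 0.7 |
|---|---|---|---|---|
| 5 points | per patient | 41 / 46 / 56% | 33 / 59 / 70% | 29 / 82 / 91% |
| 5 points | per sample | 30 / 20 / 39% | 27 / 29 / 51% | 22 / 44 / 74% |
| 10 points | per patient | 98 / 97 / 99.5% | 99 / 99 / ~100% | 99 / ~100 / ~100% |
| 10 points | per sample | 91 / 67 / 95% | 93 / 81 / 99% | 94 / 94 / ~100% |

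With no true change, the one-way test rejects in about 1.5-2%, 1% and under 1% of runs at r = 0.3, 0.5 and 0.7. The value at 0.5 differs from the 0.5% in step 2 because this is an overall test of three visits with missing samples. Complete-case repeated-measures ANOVA stays near 5%.

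**The case against.** **ANOVA may simply mean repeated-measures ANOVA, and paired tests are available.** The plan does not say that it ignores the pairing. It lists the Wilcoxon test separately from the Mann-Whitney test, which suggests the paired form, and Student's t test has a paired form too. A paired test keeps every patient with both relevant samples. In the simulation, a paired t test of baseline against day 30 had 63% power for the sustained 5-point change at r = 0.5 with per-patient loss, close to the mixed model's 70%. For a change that builds up gradually to 5 points it did better than the mixed model's overall test (65% against 57%), since it targets one contrast. This stands as far as it goes. But those tests are allowed only when appropriate, and the one sentence about intragroup comparisons names ANOVA. It also shows why the contrasts should be named.

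**Real changes will be missed.** A reader might infer this, but the documents do not support it. They give no effect size, correlation or loss pattern for this objective. The only effect size in the plan, 10 points, would be found with 97% power or more under either ANOVA with per-patient loss.

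**Most patients will be lost.** This needs independent failure at every visit, baseline included. Drop-out does not act that way.

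**The method favours a finding that aspirin withdrawal makes no difference.** That hypothesis belongs to the secondary outcome, a between-arm comparison at day 30, and the plan assigns between-group comparisons to ANCOVA. Within the arm that stops aspirin, vorapaxar starts at the same time, so its change from baseline cannot isolate aspirin under any model.

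**Conclusion.** The concern holds in a limited form. Three correlated measurements per patient, with substantial expected loss, are assigned to a method whose one-way reading has the wrong error term and whose repeated-measures reading discards usable data. In the sustained 5-point scenarios at correlations of 0.3 to 0.7, the mixed model was the most powerful of the three. At 0.5 with per-patient loss the gap is 33% or 59% against 70%. For 10-point changes with per-patient loss it almost disappears.

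These sizes rest on assumed correlations, an SD taken from the between-arm calculation, and loss completely at random. Under that kind of loss the cost is precision and power; neither ANOVA biases the estimated change. Only an exploratory objective is affected. The primary and secondary comparisons do not depend on this sentence.

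**What to change.** Replace the ANOVA sentence in the Statistical analysis plan with:

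> Within-group changes will be estimated from a linear mixed model with visit, arm, arm-by-visit and P2Y12 inhibitor stratum as fixed effects and an unstructured within-patient covariance, using all valid samples; day 7-10 versus baseline, day 30 versus baseline, and day 30 versus day 7-10 will be reported with 95% CIs.

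The third contrast is the one that speaks to stability of the effect under treatment. The plan should also state what makes a sample invalid, since the model uses all the others.

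The MIXED procedure in SPSS v22 fits this model. No extra patients, samples or software are needed. The price is slightly more analysis work and reliance on data being missing at random, a weaker condition than the completely-at-random loss that the complete-case analysis needs. Other repeated-measures methods could be defended; what matters is that method, contrasts and handling of invalid samples are fixed in advance.

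### The one-year decision to add patients has no stated calculation, parameter, blinding or maximum, and neither planned total yields 37 evaluable patients per arm at the plan's own loss rate

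*Combined protocol and SAP*

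**What the plan says.** All references are to the combined protocol and SAP.

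Study endpoints and sample size calculation gives a complete calculation for the primary comparison, with 90% power and two-sided alpha 0.05: "Assuming a 10% absolute reduction in CAT-induced MPA with a common standard deviation of 13%, 37 patients per group will be needed". It discloses where the inputs come from: "Since there are no preliminary data in this particular setting, the sample size of our study was calculated based on previous data of vorapaxar", given on top of aspirin and clopidogrel. It then allows for losses ("Considering a possible 30-35% rate of invalid results due to hemolysis or drop-out") and arrives at a total: "the three arms of treatment up to 146 patients will need to be randomized".

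Publication Strategy/Additional Information gives a different total: "we expect to enroll approximately 5-6 subjects monthly and complete enrollment in 24 months (total: 126 subjects enrolled". It goes on to say that "variability may be higher than expected and we cannot currently perform a detailed sample size calculation". Two statements follow. On the missing calculation: "We anticipate adding this to the protocol after inclusion of the study population has been completed". On extending the trial: "If the sample size after one year is estimated to be too small, additional patients will be included".

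Research Design describes an open-label study in which only the laboratory staff are blinded. The Statistical analysis plan leaves the analysis to the study group and keeps a two-tailed 0.05 threshold throughout.

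**The concern.** The timing does not work. A calculation that enters the protocol once inclusion is complete cannot support a decision on extra patients taken halfway through enrolment. The one-year sentence does not say which calculation it uses instead.

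The rule also cannot be carried out as written. It does not name the quantity to be re-estimated, say whether treatment labels are used, or set an upper limit. Neither 126 nor 146 is tied to it.

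Power is what is mainly at stake. The planning SD comes from a different background therapy, and the plan itself expects that it may be too low, so a workable resizing rule is the trial's protection. A secondary matter is that nothing written prevents the one-year estimate from using the observed treatment difference, with no adjustment of the final test.

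**Working it through.** **Inputs from the plan.** Difference 10 points, SD 13, power 90%, two-sided 0.05, three arms 1:1:1, loss 30-35%, accrual 5-6 per month, primary endpoint at about 30 days.

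**1. Reproducing 37 per arm.** The normal approximation gives n = 2 × [13 × (1.960 + 1.282)/10]² = 35.5, so 36. For the two-sample t-test, power comes from the noncentral t distribution with 2n − 2 degrees of freedom and noncentrality 10/(13 × √(2/n)). This gives 89.6% at n = 36 and 90.4% at n = 37. The plan's 37 is right.

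**2. Sensitivity to the borrowed SD** (SD values above 13 are assumed; same noncentral t).

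| SD | Power at 37 per arm | n per arm for 90% |
|---|---|---|
| 13 | 90.4% | 37 |
| 14 | 85.8% | 43 |
| 15 | 80.8% | 49 |
| 16 | 75.6% | 55 |

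**3. What the two totals deliver at SD 13.**
- 126 × 0.65/3 = 27.3 and 126 × 0.70/3 = 29.4 per arm: power 79.7-82.6%.
- 146 × 0.65/3 = 31.6 and 146 × 0.70/3 = 34.1 per arm: power 85.3-87.9%.
- 37 per arm is 111 evaluable, which needs 111/0.70 = 159 to 111/0.65 = 171 randomised.
- 146 would leave 37 per arm only at a loss of 1 − 111/146 = 24%; 126 only at 1 − 111/126 = 12%.

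**4. Information at one year.** With about one month for the endpoint to mature, 11 months at 5-6 per month is 55-66 patients. After loss, 55 × 0.65 = 36 to 66 × 0.70 = 46 values remain, or about 12-15 per arm.

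**5. Type I error by reading of the rule.** Simulation with 400,000 runs per setting, no true difference, SD 13, one look at 12-17 per arm, at least 37 per arm, and a final unadjusted t-test at 0.05. The caps of 48, 56 and 74 per arm are assumed because the plan has none.
- SD re-estimated without labels: 5.0-5.1%.
- SD re-estimated with labels: 5.0-5.2%.
- Observed difference used: 5.2-5.4%, 5.4-5.5% and 5.7-5.8% at caps of 48, 56 and 74.

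**6. What a specified rule would recover.** At SD 16, difference 10 and a floor of 37 per arm, the unlabelled-SD rule gives about 85%, 88% and 90% power at caps of 48, 56 and 74, against 76% with no resizing.

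**7. Bias of the unlabelled SD.** If both vorapaxar arms lie 10 points below control, the between-arm variance is 200/9 = 22.2. The unlabelled SD is then √(169 + 22.2) = 13.8 when the true SD is 13.

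**The case against.** The best defence is that the two sections describe one provisional plan. Study endpoints and sample size calculation admits that its inputs are borrowed, and both sections invoke the same recommendations for pilot work. On that view the later text only warns that the SD may be wrong. This largely stands. A reader might infer that the protocol both gives and denies having a sample size calculation. The documents support something milder: a provisional calculation that the later section fails to acknowledge. The defence does not resolve the timing conflict, and pilot status does not supply the missing terms of the rule, because the primary hypothesis is powered and tested.

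A second defence is that variability is the rule's only stated motive, so SD-only resizing is the natural reading and type I error is not at risk. This also stands. A reader might infer that the one-year step is an unadjusted interim efficacy test, or that the final p-value is inflated. The documents mention no interim test, and they do not say that the observed difference will be used.

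Third, 146 might be read as the maximum. It is presented as the planned total after losses, and the section that contains the extension rule plans 126.

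Finally, the mismatch of totals would exist without the extension rule. That is true. It belongs here only because a resizing rule needs one agreed starting total.

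**Conclusion.** The point holds as a matter of specification and power. The one-year decision has no stated calculation behind it, and its parameter, blinding and maximum are missing. If the SD is 14-16 and the trial stays at 37 per arm, power is 86-76% rather than 90%. At the plan's own loss rate neither total reaches 37 per arm, even at SD 13: power is 80-83% with 126 and 85-88% with 146.

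Type I error inflation is possible but small, and it is not shown: about 5% if only the SD is used, and about 5.2-5.8% if the observed difference were used at the assumed caps. These error rates rest on an unadjusted t-test, which matches the planning calculation. The Statistical analysis plan also provides for ANCOVA with covariates chosen by baseline imbalance, which was not simulated.

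The change should be made, but nothing here invalidates the primary comparison.

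**What to change.** Delete the statements that a detailed calculation cannot be done and will be added after inclusion. State that the calculation under Study endpoints and sample size calculation is provisional because its SD is borrowed. Replace the one-year sentence with a rule that says:

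- There is one re-estimation, at one year.
- It uses the SD of all available 30-day CAT-induced MPA values, pooled over the three arms, from a list without treatment labels prepared by someone who does not do the re-estimation.
- The number per arm is recomputed with difference 10, 90% power and two-sided 0.05, optionally after subtracting the planned between-arm variance of 22.2.
- The size is never reduced below the planned total randomised and never exceeds a maximum that the sponsor states.
- No between-arm comparison is run before enrolment closes.

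Use one total in place of 126 and 146. Restate the evaluable number per arm and the power it gives at 30-35% loss, or state the 159-171 randomised that 37 per arm requires, if the sponsor chooses that.

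**Cost.** The drafting is one paragraph plus the unlabelled list. The other costs fall on recruitment and precision:

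- Because the unlabelled SD contains the treatment effect, a rule with a floor of 37 per arm averages about 43 per arm when 37 suffice. That is 3 × 6 = 18 more evaluable, about 26-28 more randomised, and 4-6 more months. Subtracting 22.2 lowers the average to about 41, with power at SD 16 of 84%, 86% and 88% at caps of 48, 56 and 74.
- At 30-35% loss, a maximum of 48, 56 or 74 evaluable per arm means about 206-222, 240-259 or 317-342 randomised. At 5-6 per month that is 34-44, 40-52 or 53-68 months, against the planned 24.
- Choosing 37 evaluable per arm as the target takes 159-171 randomised, or 26-34 months, before any resizing.
- The one-year SD rests on only about 36-46 values and will be imprecise.
- The study group gives up any between-arm look during enrolment.

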In clinical trials, the most common clinical side effects of vorapaxar were anemia (5%), depression (2.4%) and rash (2.2%) [14, 18]. The most important adverse effect associated with the use of vorapaxar is bleeding. The risk of TIMI clinically significant bleeding with vorapaxar is 15.8% and 11.1% with placebo (HR 1.46; 95% CI, 1.36-1.57, $p < 0.001$); the risk of TIMI non-CABG-related major bleeding with vorapaxar is 2.8% and 1.8% with placebo (HR 1.46; 95% CI, 1.22-1.75, $p < 0.001$); the risk of intracranial bleeding (intracerebral, subdural or epidural) with vorapaxar is 1% vs 0.5% with placebo (HR 1.94; 95% CI 1.39-2.70; $p < 0.001$) [14]. However, such

bleeding prevalence occurred in the setting of long-term (3 years) trial, while our study is limited to only approximately 30 days of vorapaxar therapy. We have also excluded from the study patients at increased risk of bleeding complications [12-14]. Moreover, the use of vorapaxar in this study is limited to the intended for use population at low risk of bleeding. All clinical events described above, if they were to occur, as well as death, myocardial infarction, stroke, and urgent revascularization procedure with PCI or coronary artery bypass grafting will be recorded. Bleeding data will be collected using BARC definitions [20]. Clinical events will be evaluated by a local committee, comprised of 2 faculty members (2 cardiologists), not directly involved in the research. In the event of a report of a serious adverse event (major bleeding – defined as life-threatening: fatal, symptomatic intracranial hemorrhage, leading to a drop in hemoglobin of at least 5 g/dL, significant hypotension requiring intravenous inotropes, requiring surgical intervention, or requiring transfusion of 4 or more units of blood; non–life-threatening: substantially disabling, intraocular bleeding leading to vision loss, or requiring at least 2 units of blood; thrombocytopenia <50,000) the local committee will meet and antiplatelet treatment management will be managed according to physician recommendation.

Definition of Adverse Events

An adverse event is any unintended or undesirable experience that occurs during the course of the clinical investigation whether or not it is considered to be therapy related. This includes any newly occurring event or previous condition that has increased in severity or frequency since the initiation of study treatment. Adverse events will be followed until resolution while the patient

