remains on-study. Once the patient is removed from study, events thought to be related to the study therapy will be followed until resolution or until the patient starts a new treatment regimen.

Serious Adverse Events (SAE): An adverse event occurring while on study and considered related (reasonable possibility that the study treatment caused the adverse experience) to the study treatment that results in any of the following outcomes:

- Death
- A life-threatening adverse experience.
- A persistent or significant disability, incapacity, or is a congenital anomaly, or birth defect.
- Requires inpatient hospitalization, or prolongation of existing hospitalization.

The definition of serious adverse event also includes ‘important medical event’. Medical and scientific judgment should be exercised in deciding whether expedited reporting is appropriate in other situations, such as important medical events that may not be immediately life-threatening or result in death or hospitalization but may jeopardize the patient and/or may require medical or surgical intervention to prevent one of the other outcomes listed in the definition above. These should also usually be considered serious. Examples of such events are intensive treatment in an emergency room or at home for allergic bronchospasm; blood dyscrasias or convulsions that do not result in hospitalization; or development of drug dependency or drug abuse.

Possible benefits

The present investigation is aimed to evaluate the PD effects of vorapaxar as an add-on therapy to standard antiplatelet treatment in patients with previous MI. This study is not designed to evaluate differences in clinical benefit. However, differences in antiplatelet profiles may potentially prompt further investigations of the clinical implication of this difference by means of a larger scale clinical study.

Potential Financial Risks or Benefits

None

Conflict of Interest

[name] is a consultant for Merck, the maker of vorapaxar.

References

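### Seriousness of an adverse event is tied to judged relatedness in one section but not in another, and major cardiac events are limited to in-hospital ones in one section but not in another

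*Combined protocol and SAP*

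**What the plan says.** All places are in the combined protocol and SAP.

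- **Definition of Adverse Events, opening paragraph.** An adverse event counts whatever its presumed cause, and is followed to resolution while the patient is on study.
- **Definition of Adverse Events, SAE paragraph.** An SAE is an on-study adverse event "considered related (reasonable possibility that the study treatment caused the adverse experience) to the study treatment that results in any of the following outcomes". Four outcomes follow: death; a life-threatening experience; lasting disability, incapacity or a birth defect; and new or prolonged hospitalization. A further sentence adds important medical events and does not mention relatedness.
- **Possible Discomforts and Risk, committee sentence.** It begins "In the event of a report of a serious adverse event (major bleeding", then lists bleeding criteria and thrombocytopenia below 50,000, and ends "the local committee will meet and antiplatelet treatment management will be managed according to physician recommendation". It states no relatedness condition.
- **Possible Discomforts and Risk, recording of events.** The clinical events described there, "as well as death, myocardial infarction, stroke, and urgent revascularization procedure with PCI or coronary artery bypass grafting will be recorded". Bleeding is collected by BARC definitions. A local committee of two cardiologists with no direct part in the research evaluates clinical events.
- **Research Design.** The collection sentence starts "During study treatment in-hospital major adverse cardiac events (death, MI, stroke, and urgent revascularization procedures" and continues with "serious adverse events (bleeding and other adverse events) will be collected". Patients are recruited in cardiology clinics, and "Randomized treatment will be administered for 30 ± 3 days". The study is open label, and only laboratory personnel are stated to be blinded.
- **Study Aims.** Safety is an exploratory aim.

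**The concern.** Seriousness describes the outcome of an event; relatedness is a judgement about its cause. The SAE paragraph merges the two, so a death or hospitalization judged unrelated is not an SAE under its main definition. The plan applies no such filter to ordinary adverse events, so the rule is stricter for serious events than for minor ones. The risk section then uses the same term for a different set of events with no causal condition.

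The second problem is location. Outpatients treated for about a month will spend nearly all of that time outside hospital unless an event brings them in. A rule that collects only in-hospital cardiac events does not fit that setting, and it disagrees with the risk section.

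At stake is whether staff at this site classify the same event in the same way throughout the study. The documents do not say who judges relatedness. In an open-label trial, that person may know the assignment.

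**Working it through.** No arithmetic beyond counting applies, and the plan states no figure to reproduce. The check sets the sections side by side.

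**Part 1: SAE definition**

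1. SAE paragraph: the relatedness condition stands before the outcome list and governs all of it, so 4 of 4 listed outcomes are conditioned.
2. Risk section: none of the bleeding or platelet criteria is conditioned.
3. The important-medical-event sentence extends the kinds of outcome that count, mainly to events that do not end in death or hospitalization. It neither lifts nor repeats the relatedness condition for the four listed outcomes, so it does not settle the matter.
4. Neither set contains the other, as the first two rows of the table show.

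**Part 2: scope of cardiac events**

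1. Research Design names four components (death, MI, stroke, urgent revascularization), and the in-hospital qualifier applies to 4 of 4.
2. The risk section names the same four, and the qualifier applies to 0 of 4.
3. The treatment window runs from 30 − 3 = 27 days to 30 + 3 = 33 days. No planned hospital stay is described.

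**Example events, read literally**

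| Event | Research Design | Risk section | SAE paragraph (main definition) |
|---|---|---|---|
| Listed major bleed, hospitalized, judged unrelated | Collected (bleeding) | SAE; committee meets | Adverse event, not SAE |
| Non-bleeding hospitalization, judged related | Collected as SAE | Not on the SAE list | SAE |
| Out-of-hospital death from MI, judged unrelated | Outside the cardiac-event list | Recorded; not on the SAE list | Adverse event, not SAE |

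The third row shows the two parts together: outside the cardiac-event list in one section, not an SAE in another, but recorded under the risk section. The event is therefore not lost if all sections are followed. What changes between sections is its label and, for the first row, possibly whether the committee is convened.

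**The case against.** The strongest reply is that nothing goes missing.

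- **Other routes exist.** The in-hospital qualifier grammatically covers only the cardiac events. The same sentence also collects "serious adverse events (bleeding and other adverse events) will be collected" with no location limit. The adverse event definition ignores cause, and the risk section records the four cardiac events wherever they occur. Following the broader section satisfies both. This stands: loss of events is not shown.
- **The risk-section list may not be a definition.** It sits inside a sentence about when the committee meets and may be only that trigger. It is also silent on relatedness rather than expressly waiving it. This is plausible, but the text uses the term serious adverse event and does not say that the list has a narrower purpose.
- **Few bleeds may be affected.** In patients taking two or three antithrombotic drugs, a major bleed would seldom fail a test of reasonable possibility. That is fair for bleeding, but less so for deaths and hospitalizations from other causes.
- **There is a safeguard.** Two cardiologists with no direct part in the research evaluate clinical events, whatever the judged cause. This reduces the worry about open-label judgement. It does not remove it, because they are not stated to be blinded.

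A reader might also infer that SAE counts will be biased between arms, since one regimen is simply to "continue DAPT with aspirin and prasugrel/ticagrelor" and relatedness there concerns drugs already being taken. The documents do not support that. Continued DAPT is itself one of the three randomized regimens, so relatedness can be judged there too. Neither the endpoints section nor the Statistical analysis plan specifies a comparison of SAEs by arm. The cardiac events and BARC bleeding that the plan names as safety data do not pass through the relatedness filter. Nothing in the text gives a direction or size.

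**Conclusion.** The point holds as an inconsistency in definitions that should be corrected. One section makes every listed SAE outcome depend on judged relatedness, and another describes SAEs without that condition. One section limits four cardiac events to hospital, and another records the same four anywhere. The result is misclassification of serious events and an unclear cardiac-event scope, both confined to exploratory safety data.

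This rests on reading the sections literally, and on no stated order of precedence between them. If the risk-section list is only a meeting trigger and the Research Design sentence only a summary, the contradiction narrows. The relatedness condition on SAEs would still remain.

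The documents give no event rate from which to size the effect, so none is claimed. The primary endpoint (CAT-induced MPA at 30 ± 3 days), the sample size and the significance level are unaffected.

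**What to change.** 1. **Definition of Adverse Events.** Define an SAE by the listed outcomes, or as an important medical event, regardless of judged relatedness. Record relatedness in a separate field on the event form.
2. **Research Design.** Delete the in-hospital qualifier so that the cardiac-event scope matches the risk section. Keep the statement that bleeding (by BARC) and other adverse events are collected, and add that SAEs are as defined under Definition of Adverse Events. Replacing the existing words with a cross-reference alone could remove that section's statement that bleeding and non-serious events are collected.
3. **Possible Discomforts and Risk.** State whether the bleeding and thrombocytopenia list serves only to convene the committee, and reconcile its use of the SAE term with the definition. No treatment-management rule needs to change.

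The cost is wording in three sections, one extra form field and a few more event forms. No analysis or sample size changes.
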